Radiologic tumor assessment will be performed at baseline, cycle 3 day 1, cycle 5 day 1 and at the end of every 3 cycles beyond cycle 5 (one cycle = 21 days). All patients including those removed from the study due to unacceptable toxicity, will undergo radiologic tumor assessment within 30 days of the time of discontinuation (End of treatment). If a scan is performed within 30 days of end of treatment is available, the previous scan will be accepted. Patients who show disease progression at the first instance could continue to receive the treatment for up to 2 more cycles depending upon the percentage of increase in the tumor. Patients up to 30% increase in tumor burden would be allowed to continue the treatment until the second confirmatory scan if the patient is deriving clinical benefit in the treating Physician's opinion. Patients who continue treatment beyond progression would undergo another confirmatory scan at the end of 2 more cycles and if the progression is confirmed they will be come off the study.

4 Eligibility Criteria

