4.6 Subject Registration

In order to begin the patient registration process, the site must obtain a slot for the candidate patient from Oncoceutics. At the time of receipt of the signed consent form, Oncoceutics medical monitor must be notified via email to initiate eligibility review. The study staff must include de-identified patient source documentation, the completed New Patient Registration Form (provided by Oncoceutics) and a tentative therapy start date. Correspondence from the Sponsor for patient registration approval will be granted within 48 hours of receipt of adequate documentation.

Registration approval will be valid for 7-business days from receipt of approval. If the potential patient is not treated within those 7 business days, a new registration form must be submitted to determine eligibility.

A patient identifier will be assigned at the time of approval. Screening and eligibility MUST be entered into Redcap EDC within 7-business days of screening visit.

5 Treatment Plan

Treatment will be administered on an outpatient basis. Treatment will be administered as described below. Dose delays and modifications should only be done following protocol guidelines described in section 6.0. If treatment delays are more than 14 days due to toxicity study therapy will be discontinued.

Regimen description					
Arm	Agent	Dose	Route	Schedule	Cycle Length
A & B	ONC201	625mg	Oral	Once per week	3 weeks
С	ONC201	625mg	Oral	Twice per week on two	3 weeks
				consecutive days	

5.1 **Treatment Administration**

One treatment cycle will be defined as 21 days, corresponding to 3 doses of ONC201 (i.e., one cycle is 3 weeks) for Arm A and B or 6 doses in Arm C. Beyond cycle 1 week 1 dose(s), ONC201 capsules will be dispensed on day 1 of every cycle thereafter to be taken at home. Patients must complete study drug diary to keep a log of the drug intake. Any unused drug should be returned to the site. Any missed doses should be recorded. At home patients must take the drug as indicated, however if the drug is missed for reasons not related to adverse events +/- 2 days are allowed. The capsules should be swallowed as whole and should not be chewed or broken.

Patients should take designated capsules of ONC201 at approximately the same time on each drug administration. Patients will be instructed to not eat for 2 hours pre and 2 hours post dosing. If the patient vomits after taking ONC201, they should not retake the dose.

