5.5 Criteria for Discontinuation

Patients will be removed from study when any of the criteria listed in Section 5.3 applies. Patients can also be removed from the study for non-compliance. The reason for study removal and the date the patient was removed must be documented in the medical record and case report form.

6 Dose Modifications

The descriptions and grading scales found in the revised NCI Common Terminology Criteria for Adverse Events (CTCAE) version 4.03 will be utilized for dose delays and dose modifications

Below are dose modifications (Table 6.1 and 6.2) for adverse events that are attributable to study drug, including: nausea, vomiting, diarrhea, neutropenia, and thrombocytopenia. If a patient experiences other adverse events, or several adverse events and there are conflicting recommendations based on Grade, the investigator will use the recommended dose adjustment that reduces the dose. Dose modifications will be made based on an adverse event that occurs during any time during a cycle.

Criteria for disrupting treatment, dose modification, or discontinuation are listed in Table 6.1. Dose modifications are per the clinical judgment of the investigator and agreement of the subject, the treatment will be resumed according to the table below. Dose modification may not be required for adverse events that are clinically manageable.

Table 6.1 Dose adjustment rules for Adverse Events (AEs), including Nausea,
Diarrhea, Neutropenia, Thrombocytopenia, and Other AEs. Alopecia does not
require dose adjustments.

CTCAE Grade	Management/Next Dose for ONC201	
\leq Grade 2	No change in dose	
Grade 3 or 4*	Hold until \leq Grade 2. If resolved to \leq Grade 2 within 7 days, resume dosing at 500mg if previously dosed at 625mg or resume dosing at 375mg if previously dosed at 500mg.**	
*Patients requiring a delay of >3 weeks should go off protocol therapy. Patients with		
the dose modification is for each dose		
** Patients requiring $>$ two dose reductions should go off protocol therapy.		

Participants who experience an adverse event that requires a treatment delay or dose reduction should be monitored with appropriate laboratory testing or other clinical evaluation at least weekly until resolution. If a grade 3 or 4 adverse event does not resolve within 3 weeks, the patient will be required to come off study, and the interval for testing may be reduced after consultation and written approval by Sponsor.

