For holds for reasons other than treatment related toxicities, if the participant does not meet criteria to resume treatment within 6 weeks of the event precipitating the hold, the study agent(s) may be restarted with approval from the Sponsor, as long as there has been no significant evidence of disease progression (e.g., by clinical findings, symptoms, tumor markers) during the treatment interruption.

7 Study Agent Information

The study drug ONC201 is provided as 125 mg free base (approximately 150 mg of dihydrochloride), with or without microcrystalline cellulose, filled into hydroxypropyl methylcellulose (HPMC) capsule shells. Alternative strengths may be manufactured and additional excipients may be used.

The ONC201 drug product capsules are intended for oral administration. The product is stored in a multi-dose container. The capsules are packaged in high-density polyethylene (HDPE) white opaque bottles, closed with an induction seal and capped with a white ribbed SecuRx® polypropylene (PPE) cap.

The capsules are to be stored in the original closed container at room temperature (15 to 30° C). The study drug bottle label bears the following information. If alternative strengths are manufactured, the dosage on the label will be inserted in place of '125 mg'.

ONC201 Capsu	les, 125 mg
For Oral Us	e Only
Caution: New DrugLimited by law to investiga	r Federal (or United States) tional use.
Storage: Preserve in original tight temperature (15	tly closed containers at room 5 to 30°C)
Sponsor: Oncoc	eutics, Inc.
Batch # xxx-xxx-xxxx-xx	Mfg date: XX-XXXX

7.1 **Drug Substance Description**

Compound Code(s)	ONC201•2HCl
Alternative Name(s)	ONC201 TIC10 NSC-350625
Chemical Name(s)	7-benzyl-4-(2-methylbenzyl)-1,2,6,7,8,9- hexahydroimidazo[1,2-a]pyrido[3,4- e]pyrimidin-5(4H)-one 2HCl
Molecular Formula	C24H26N4O (free base) C24H26N4O•2HCl (salt)

Molecular Weight	386.49 (free base) 459.41 (salt)
Molecular Structure	

7.2 **Drug Product Description**

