For Arm C: Blood draws taken at baseline (pre-dose), 2 hours ± 15 minutes, 24 ± 1 hours (pre-day 2 dose), 26 ± 2 hours, 48 hours ± 3 hours, 72 hours ± 12 hours, and Day 8 and 15 ± 24 hours following the first administration of ONC201. Blood will also be collected predose for Cycle 2, Cycle 3 and every odd cycle beyond Cycle 3.

Refer to lab manual for collection window of samples. Blood will also be collected at the end of treatment visit for correlative studies. Immune cytokines and effectors will be assessed on serum samples obtained for pharmacodynamic analyses.

Refer to lab manual for Biospecimens processing and handling requirements.

8.3 **Blood for immune cell studies**

Peripheral blood mononuclear cells (PBMCs) will be harvested and investigated for effects of ONC201 on the immune system. One EDTA tube of blood will be collected at the same time points as the red-top tubes are collected: Baseline and 2 hours, 24 hours, 48 hours, and 72 hours after the first dose of ONC201; Cycle 1 Day 8; Cycle 1 Day 15; pre-dose for the first day of cycle 2, cycle 3 and every odd cycle beyond cycle 3. Blood will also be collected at the end of treatment visit for correlative studies. Collection of PBMCs is not required for Arm C.

8.4 **Blood for pharmacokinetics**

The plasma obtained prior to the isolation of PBMCs (see Section 8.3) will be used to determine concentration of ONC201. No additional blood samples will be collected from the patient for these studies. For Arm C, plasma for pharmacokinetics will be collected at baseline (pre-dose), 2 hours \pm 15 minutes, 24 \pm 1 hours (pre-day 2 dose), 26 \pm 2 hours, 48 hours \pm 3 hours, 72 hours \pm 12 hours, and Day 8 and 15 \pm 24 hours following the first administration of ONC201. Blood will also be collected pre-dose for Cycle 2, Cycle 3 and every odd cycle beyond Cycle 3.

9 Study Calendar

Study visits and procedures may be scheduled with a +/-2 business day window except for Screening procedures (-14 days) and neuroimaging (MRI/CT) Screening, Cycle3 and every odd cycle day 1 (+/-7 days). One treatment Cycle is defined as 3 weeks (21 days).

Study Activity	Screening	C1D1	C1D2	C1D3	C1D8	C1D9	C1D10	C1D15	C1D16	C2D1	C2D2	Cycle 3, and every odd cycle, day 1 ⁸	Off- treatment	Follow-up 30 days (+/- 3 days) ⁵	Survival Follow Up (30 +/- 7 days)
Informed Consent	Х														
Medical History	Х														
Inclusion/exclusion criteria	х														
Concurrent meds ¹	х	Х								Х		Х	Х		

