11.1 Response Evaluation Criteria in Solid Tumors (RECIST)

The Response Evaluation Criteria in Solid Tumors (RECIST v 1.1) criteria will be used for objective tumor response assessment. Response assessment would be performed at C3D1, C5D1 and at the end of every 3 cycles beyond cycle 5. All patients, including those removed from the study due to unacceptable toxicity, would undergo radiologic tumor assessment at the time of discontinuation (End of treatment). Patients who show disease progression at the first instance could continue to receive the treatment for up to 2 more cycles if the increase in tumor burden is up to 30%. Patients who continue treatment beyond

progression would undergo another confirmatory scan at the end of 2 more cycles, and if the progression is confirmed, they will be come off the study.

11.2 **Definitions**

Evaluable for adverse events. All patients will be evaluable for adverse events from the time of their first treatment with ONC201.

Evaluable for progression-free survival. All Arm B patients who have received at one dose of ONC201 will be considered evaluable for progress-free survival as the primary endpoint.

Evaluable for objective response. Only those patients who have measurable disease present at baseline, have received at least one cycle of therapy, and have had their disease reevaluated will be considered evaluable for response. These patients will have their response classified according to the definitions stated below. (Note: Patients who exhibit objective disease progression prior to the end of cycle 1 will also be considered evaluable.)

Evaluable Non-Target Disease Response. Patients who have lesions present at baseline that are evaluable but do not meet the definitions of measurable disease, have received at least one cycle of therapy, and have had their disease re-evaluated will be considered evaluable for non-target disease. The response assessment is based on the presence, absence, or unequivocal progression of the lesions.

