The duration of overall CR is measured from the time measurement criteria are first met for CR until the first date that progressive disease is objectively documented.

Duration of stable disease: Stable disease is measured from the start of the treatment until the criteria for progression are met, taking as reference the smallest measurements recorded since the treatment started, including the baseline measurements.

11.7 **Progression-Free Survival**

Progression-free survival (PFS) is defined as the duration of time from start of treatment to time of progression or death, whichever occurs first. Progression-free survival (PFS) is defined as the time from registration to objective disease progression or death, whichever occurs first. PFS2 will be defined as the percentage of patients who exhibit PFS for >8 weeks (>56 days). Patients who have not progressed or died and are lost to follow up at 2 months will be replaced.

12 Statistical Considerations

12.1 **Primary Endpoint and Interim analyses**

Arm A and C will assess intratumoral drug concentrations and pharmacodynamics. Arm B will assess progression-free survival rate at two month following treatment initiation as primary endpoint. Patients with biopsiable disease may represent a biased subset of the overall target population since some sites of metastases will not be amenable to biopsy and therefore comparing these patients' outcomes to historical controls may not be appropriate. For this reason, only patients in Arm B will be evaluated for the primary endpoint of PFS2.

No interim analyses will be performed for Arm A or C. Pharmacodynamic effects will be evaluated by assessment of tissue biomarkers based on mechanism of action and preclinical tumor cell sensitivity studies. IHC analyses for biomarkers such as ATF4, CHOP, and DR5 will be summarized using descriptive statistics.

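### Tumor scans follow cycle days, and the plan does not say whether a dose hold moves them; if it does, an Arm B patient who progressed early can be scored as a PFS2 success

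*Combined protocol and SAP*

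**What the plan says.** **Scan timing.** Section 3 states "Radiologic tumor assessment will be performed at baseline, cycle 3 day 1, cycle 5 day 1", adding that a cycle is 21 days. Section 11.1 repeats the rule: "Response assessment would be performed at C3D1, C5D1 and at the end of every 3 cycles beyond cycle 5". Section 9 gives the imaging window as "Cycle3 and every odd cycle day 1 (+/-7 days").

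**Cycle.** Section 5.1: "One treatment cycle will be defined as 21 days, corresponding to 3 doses of ONC201" (Arms A and B). Section 7.3.3 says that a dose more than two days late is skipped, not made up.

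**Permitted interruptions.**
- Section 5 ends therapy when a toxicity delay exceeds 14 days.
- The footnote to Table 6.1 says "Patients requiring a delay of >3 weeks should go off protocol therapy".
- For holds not caused by treatment-related toxicity, Section 6 allows restart with sponsor approval even "if the participant does not meet criteria to resume treatment within 6 weeks of the event precipitating the hold", provided there is no significant evidence of progression.

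**Endpoint.** Section 11.7: "PFS2 will be defined as the percentage of patients who exhibit PFS for >8 weeks (>56 days"). It gives two starting points for PFS, start of treatment and registration ("Progression-free survival (PFS) is defined as the time from registration to objective disease progression or death, whichever occurs first"). Section 12.1 counts from treatment initiation. Arm B continues if at least 5 of 10 patients succeed, and is positive if at least 14 of 24 do.

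**The concern.** A progression that must be objectively documented is dated by the scan that shows it. PFS2 is therefore reliable only if the first post-baseline scan falls on or before day 56 for every patient. A rule written in cycle days gives that assurance only if cycles keep running through a hold, and the plan does not say whether they do.

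If a hold defers cycle 3 day 1, the scan is deferred too. A patient who had already progressed at week 6 but is first scanned after day 56 has a recorded PFS of more than 56 days. She counts as a success because her dosing was interrupted, not because the drug worked. The error runs one way, there is no control arm to offset it, and it enters both the futility look and the final decision.

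No other rule catches the case. The end-of-treatment scan covers patients who stop, not those who are held and resume. Section 11.2 makes every dosed Arm B patient evaluable, and Section 11.7 replaces only those lost to follow-up. No section says how to score progression first seen on a scan after day 56.

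**Working it through.** **1. The plan's own design (Section 12.1).** Inputs: null 40%, alternative 70%, continue at ≥5/10, success at ≥14/24.

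P(success | p) = Σ over x = 5..10 of Bin(x; 10, p) × P(Y ≥ 14 − x), with Y ~ Bin(14, p). P(stop early | p) = P(X ≤ 4), with X ~ Bin(10, p).

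- p = 0.40: type I error 0.0482, early stopping 0.633.
- p = 0.70: power 0.901.

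This reproduces the stated 5%, 63.3% and 90%.

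**2. When the first post-baseline scan falls.** Days from first dose = 2 × 21 + s + w = 42 + s + w, where s is the shift of cycle 3 day 1 and w is the window, −7 to +7. The scan is too late if the total exceeds 56.

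| Shift s | Nominal day | Range with window | Past day 56? |
|---|---|---|---|
| 0 | 42 | 35–49 | no |
| 7 | 49 | 42–56 | no |
| 8 | 50 | 43–57 | only with late use of the window |
| 14 | 56 | 49–63 | only with late use of the window |
| 15 | 57 | 50–64 | yes, at the nominal day |
| 21 | 63 | 56–70 | yes, at the nominal day |
| 42 | 84 | 77–91 | yes |

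Section 5's 14-day toxicity limit therefore reaches past day 56 only with the window. The 3-week limit in Table 6.1 reaches it without. The 42-day row applies only to holds not caused by treatment-related toxicity.

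**3. Which patients change status.** Undelayed scans fall at days 42 and 84. A patient who progresses between days 42 and 56 is normally first seen at day 84, so she already counts as a success without any hold. A hold newly converts only those who had progressed by day 42.

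**4. Effect on type I error.** Assumptions, none of them in the documents: exponential PFS with 40% at day 56; 90% of failures are radiographic; a share h of Arm B has its first scan after day 56, independently of progression.

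- Progression-free at day 42: 0.40^(42/56) = 0.503, so failures by day 42 are 0.497.
- Effective null rate = 0.40 + 0.497 × 0.9 × h.

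| h | Patients of 24 | Effective null rate | Type I error | Early stopping under null |
|---|---|---|---|---|
| 0 | 0 | 0.400 | 4.8% | 63.3% |
| 5% | 1.2 | 0.422 | 7.5% | 57.6% |
| 10% | 2.4 | 0.445 | 11.2% | 51.8% |
| 20% | 4.8 | 0.489 | 21.7% | 40.3% |

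The calculation starts from 40% to isolate the effect of holds. It leaves out the effect of having no scan between days 42 and 84.

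**The case against.** The strongest objection is that nothing says a hold moves cycle 3 day 1. Sections 3, 5.1 and 9 all define a cycle as 21 days, the calendar footnote fixes weekly dosing on days 1, 8 and 15 of a three-week cycle, and Section 7.3.3 skips late doses. Read together, held doses drop out while the clock runs, and the scan stays at day 42. This stands as a fair reading, but not the only one. Section 5.1 also equates a cycle with three doses, and Section 7.3.3 has the patient dosed in clinic on day 1 of each cycle, so a site could defer that visit, and the scan, during a hold. The skipped-dose rule concerns single doses and does not address cycles or scans.

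A reader might also infer that toxicity holds of up to three or six weeks are simply allowed. The documents do not support that. The 14-day and 3-week limits contradict each other, Table 6.1 describes resumption only after resolution within 7 days, and the 6-week text excludes treatment-related toxicity. A 7-day shift with the full window reaches day 56, not beyond it.

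Finally, one might apply the shift to all radiographic failures by day 56 (0.60 × 0.9 × h). That gives 8.2%, 13.0% and 27.4% for h of 5%, 10% and 20%, but it includes the day 42–56 progressors whom the undelayed schedule already scores as successes.

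**Conclusion.** The point holds as an ambiguity in how the primary endpoint is assessed. The plan does not settle whether scans move with a hold. If they do, permitted interruptions can push the first post-baseline scan past day 56 and turn a patient who had progressed by about day 42 into a PFS2 success. This needs a shift of at least 15 days, or of 8 to 14 days with late use of the window; 7 days or less cannot do it.

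The direction is certain: any such error favours the drug. The size is not. Type I error of about 7.5%, 11.2% or 21.7% rests on assumed shares of 5%, 10% or 20%, exponential PFS and 90% radiographic failures. The documents give no hold rate, and Section 1.5 describes earlier treatment as generally well tolerated. It would be too strong to say that toxicity holds will create successes or that the design's error rate is already broken by this route. This is a low-cost correction that should be made, not a demonstrated failure of the design.

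**What to change.** 1. In Sections 3, 9 and 11.1, time all tumor scans in calendar days from first dose, irrespective of dose holds or cycle delays.
2. In Section 12.1, pre-specify that an Arm B patient whose first post-baseline scan is after day 56 and shows progression counts as a PFS2 failure. State that this is a conservative convention, because some of these patients may truly have progressed after day 56.
3. Reconcile the delay limits in Section 5 and Table 6.1, and keep one starting point for PFS in Section 11.7, so that the scan clock and the endpoint clock agree.

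With items 1 and 2 in place, holds can no longer convert these failures to successes, and the design keeps its 4.8% type I error and 90% power against this source of bias.

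**Cost.** Wording only, with no added scans. Some scans will not coincide with a delayed day-1 visit, and observed PFS2 may be slightly lower.

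This does not cure the separate problem that undelayed scans at days 42 and 84 leave none near day 56.

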4.1 Inclusion Criteria

- 1. Histologically confirmed metastatic or recurrent Type II EC (serous, clear cell, carcinosarcoma, adenosquamous and mixed histologies). For patients with tumors that have mixed histologies, the tumor should have evidence of some tumor cells with Type II endometrial cancer features.
- 2. Patients must have measurable disease, defined as at least one lesion that can be accurately measured in at least one dimension in accordance with RECIST criteria v. 1.1 as described in detail in section 11.
- 3. Availability of at least 12 unstained slides from archival FFPE tumor tissue. Available archived tissue biopsies will be provided for correlative studies.
- 4. For Arm A and C, patients must have disease that is amenable to biopsy and must be willing to provide consent for a tumor biopsy at baseline (within 30 days of beginning ONC201) and at least 1 on-treatment tumor biopsy.
- 5. Must have radiographic disease progression after at least 1 line of systemic cytotoxic therapy for metastatic disease or with progression within 12 months of completing adjuvant chemotherapy.

- 6. Age \geq 18 years.
- 7. ECOG performance status of 0, 1, or 2.
- 8. Patients must have adequate bone marrow, hepatic and renal function as defined below:

Leukocytes	\geq 3,000/mcL
Absolute neutrophil count	\geq 1,500/mcL
Platelets	\geq 100,000/mcL
Total bilirubin	≤1.5 ULN
AST/ALT (SGOT/SGPT)	\leq 2 ULN
Creatinine	≤1.5 ULN
OR	
Creatinine clearance	\geq 60 Ml/min/1.73 m ² for patients
with creatinine levels above UL	N calculated using Calvert formula

- 9. Life expectancy at least 3 months.
- 10. Ability to understand and willingness to sign a written informed consent and HIPAA consent document.
- 11. Patients must be surgically sterile or be postmenopausal, or must agree to use effective contraception during the period of the trial and for at least 90 days after completion of treatment.

